Study Protocol Document

Community Collaboration to Advance Racial/Ethnic Equity in CRC Screening

NCT Number: NCT05714644

10/02/2025

Description of Study:

This is a pragmatic, multilevel randomized clinical trial with randomization at the level of the Community Health Center (CHC) to compare two population outreach approaches to increase colorectal cancer (CRC) screening uptake among diverse and multilingual patients: (1) mailed FIT outreach with text reminders, and (2) mailed FIT-DNA with the standard manufacturer's patient support program. Participants with an abnormal FIT or FIT-DNA result are offered telephone navigation to encourage colonoscopy completion. We hypothesized that (1) CRC screening participation would increase in both study arms; and (2) that the FIT-DNA arm would have higher participation given the centralized patient support program and appeal of the 3-year screening interval.

Objective:

The objective of this study was to compare two mailed population outreach approaches to increase colorectal cancer screening uptake among screening-eligible adults in community health centers. The primary outcome was CRC screening test completion rate using any screening modality (FIT, FIT-DNA, colonoscopy) at 90 days after the screening test was mailed in each study arm. Secondary outcomes included the screening completion rate at 180 days and the rate of completion of follow-up colonoscopy within 180 days (6 months) of an abnormal stool test result among participants with an abnormal screening test result.

Design:

This was a cluster randomized controlled trial conducted in 8 CHCs and an additional site in a non-randomized parallel protocol.

Methods:

Individuals in the designated CHCs were eligible if they were: (1) age 45 to 75; (2) overdue for CRC screening (no FIT or fecal occult blood test [FOBT] in the past year, FIT-DNA in the prior 3 years, or colonoscopy in the past 10 years); (3) under the active care of a primary

care provider at the site; and (4) spoke English or Spanish. Individuals were excluded who did not have a physical mailing address or phone number listed in the electronic health record (EHR), had prior documentation of CRC, Crohn's Disease, or ulcerative colitis, or had prior abnormal colonoscopy result (i.e., prior adenoma, sessile serrated lesion).

Randomization was limited to the 8 CHCs in Boston and LA. We used CHC-level cluster randomization to minimize the chance of contamination within practices. Within each region, we considered the permutations of assigning the four CHCs into two arms. We chose the permutation with the closest patient volume, racial distribution, and baseline CRC screening rate, then randomly assigned the groups to one of the two study arms. Neither patients nor sites were blinded to the allocation.

In both arms, participants received an invitation letter that provided elements of informed consent via mail with the opportunity to opt out of the study. Intervention components were delivered in English or Spanish, based on patient preference as recorded in the EHR.

FIT-DNA arm. Participants were mailed a FIT-DNA kit from Exact Sciences with instructions on how to complete and return the kit to their laboratory using a standard pre-paid mailer. Participants in this arm received the standard patient support program delivered by Exact Sciences, including telephone calls, text messages, and emails in the users' preferred language to encourage completion of the kit.

FIT arm. Patients received a primer text message to inform them that a FIT kit would soon arrive at their home address. Participants then received the FIT kit in a separate mailing with a graphic instruction sheet. Two additional reminder text messages were sent. In each CHC, we used the FIT kit brand already in routine use (Boston: Polymedco; LA and SD: Hemosure iFOB test).

Navigation for patients with abnormal FIT or FIT-DNA. Participants in Boston and LA with an abnormal FIT or FIT-DNA result were offered standardized phone navigation by non-clinical team members proficient in English or Spanish, to address barriers to colonoscopy and encourage completion. In SD, patients with an abnormal FIT or FIT-DNA result received usual care follow-up, which included non-standardized outreach from clinical staff.

Statistical Analysis Plan

Community Collaboration to Advance Racial/Ethnic Equity in CRC Screening

NCT Number: NCT05714644

8/20/2025

All sociodemographic, clinical, and outcome data were obtained from electronic health record EHR. Patient characteristics will be presented as means with standard deviations (continuous) or frequencies and proportions (categorical). For the RCT, the primary intent-to-treat analysis included all study participants who did not opt-out from the Boston and LA CHCs. A secondary analysis used a propensity score matched sample to ensure balance between the two groups on age, gender, race/ethnicity and insurance status. We also conducted a sensitivity analysis excluding participants who might have completed screening before receiving the mailed screening kit, defined as within 7 days after the kit was sent. A final analysis included participants from SD in the FIT-DNA arm.

We compared the proportions of eligible individuals who participated in screening within 90 days or 180 days between study arms using logistic regression models with the generalized estimating equations to account for the correlated nature of data within CHCs, adjusting for age and race/ethnicity, which were unbalanced between the two arms. We compared time to screening participation between the two arms using a log-rank test. We also explored the heterogeneity of treatment effect by conducting subgroup analyses for pre-specified subgroups of interest (region, race/ethnicity, age, and language) and added insurance subgroups as a post hoc comparison. Among participants who returned stool tests within 180 days, we compared the distribution of test results between study arms using Fisher's exact tests. Among those with an abnormal stool test result, we compared the rate of colonoscopy completion within 180 days by arm and region using Fisher's exact tests and compared time to colonoscopy completion between the two arms using a log-rank test. All analyses were conducted using SAS version 9.4 (Cary, NC).

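### The propensity-matched secondary analysis does not list region, the randomization stratum, so it can unbalance region between arms; the primary GEE shares the gap

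*SAP*

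**What the plan says.** The Protocol's Methods (randomization paragraph) says "Randomization was limited to the 8 CHCs in Boston and LA". It continues: "Within each region, we considered the permutations of assigning the four CHCs into two arms". One split per region was picked for balance ("We chose the permutation with the closest patient volume, racial distribution, and baseline CRC screening rate"), and a random draw decided which group received which intervention. The unit of allocation is therefore the CHC and the stratum is region.

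The SAP's first paragraph defines the primary population: "the primary intent-to-treat analysis included all study participants who did not opt-out from the Boston and LA CHCs". It then adds the secondary analysis: "A secondary analysis used a propensity score matched sample to ensure balance between the two groups on age, gender, race/ethnicity and insurance status". No matching ratio, caliper, replacement rule or within-region restriction is given.

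The SAP's second paragraph describes the outcome model as logistic regression with "generalized estimating equations to account for the correlated nature of data within CHCs", "adjusting for age and race/ethnicity, which were unbalanced between the two arms". Region is not listed as a covariate there either. It does appear as a pre-specified subgroup and in the colonoscopy comparison.

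**The concern.** Every allocation the design permits puts two CHCs per arm in Boston and two in LA, in groups chosen for similar patient volume. Approximate region balance is therefore built in. Matching on patient characteristics selects who stays in the sample. When a matching variable is related to region, and that relation differs between the arms, a selection that ignores region keeps different proportions of Boston and LA patients in each arm.

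The SAP records one ingredient: age and race/ethnicity were unbalanced between arms, so matching will act on them. The other ingredients are a different demographic mix in Boston and LA and a different background uptake. Both are plausible, but neither is documented.

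The matched analysis is there to reassure readers about imbalance. If it disagreed with the primary result, a reader could not tell correction of patient-level imbalance from a shift in region mix. If it agreed, the two analyses might simply share the same omission.

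**Working it through.** The plan states no sample size, matched number or uptake by region, so there is no figure to reproduce. The check has two parts: the design, and an illustration in which all inputs are assumed.

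**Design.** Four CHCs can be split into two pairs in C(4,2)/2 = 3 ways. Each split can be assigned to arms in 2 ways. All of these leave two CHCs per arm in the region.

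**Illustration.** Take 100 patients per arm, 50 per region, and one binary matching variable (Hispanic or not). The assumed Hispanic share is 30% in both Boston groups, and 90% (arm A) v 60% (arm B) in LA. Uptake depends on region only, so the true arm difference is zero.

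| | Boston Hispanic | Boston non-Hispanic | LA Hispanic | LA non-Hispanic |
|---|---|---|---|---|
| Arm A | 15 | 35 | 45 | 5 |
| Arm B | 15 | 35 | 30 | 20 |

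*1. Matching 1:1 without region.*
- Hispanic pairs: min(60, 45) = 45. Non-Hispanic pairs: min(40, 55) = 40. Retained: 85 of 100 per arm.
- Boston share, arm A: (45 × 15/60 + 40 × 35/40)/85 = (11.25 + 35)/85 = 54.4%.
- Boston share, arm B: (45 × 15/45 + 40 × 35/55)/85 = (15 + 25.45)/85 = 47.6%.
- Gap: 6.8 points, where before matching it was 0 (50% v 50%).
- Spurious arm difference = gap × regional difference in uptake: 0.068 × 10 = 0.7 points; 0.068 × 20 = 1.4 points.

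*2. Regression on everyone, adjusting for arm and ethnicity but not region.*
- A linear model weights the within-stratum arm differences by n_A n_B/(n_A + n_B).
- Hispanic: the difference in Boston share is 15/60 − 15/45 = −8.33 points, weight 60 × 45/105 = 25.71.
- Non-Hispanic: 35/40 − 35/55 = +23.86 points, weight 40 × 55/95 = 23.16.
- Weighted mean: (25.71 × −8.33 + 23.16 × 23.86)/48.87 = 6.9 points.
- Spurious difference: 0.069 × 10 = 0.69 points; 0.069 × 20 = 1.38 points.
- A logistic model standardised to the full sample gives the same values to this accuracy (independence working correlation; another structure could differ). Adding region returns zero. The unadjusted comparison is also zero.

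*3. Matching 1:1 within region.*
- Pairs: Boston 15 + 35, LA 30 + 5. Total 85, the same retention as in step 1.
- Boston share: 50/85 = 58.8% in both arms, so the region gap is zero.

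**Range under other assumptions.** Seven further scenarios were run, each with equal region-by-arm cells and one binary variable. Matching without region left region balanced in 2 and unbalanced it in 5. The largest gap was 45.8% v 54.2% Boston (8.4 points, about 0.8 points of spurious difference for a 10-point regional gap in uptake). Matching within region gave equal region shares in all 7. It discarded the same number of patients or more; for example, 20% instead of 0% with Hispanic shares by arm of 30% and 50% in Boston, and 80% and 60% in LA.

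**The case against.** The strongest reply is that this is not a defect of matching. The spurious difference in step 1 is absent only from a crude comparison, and the SAP's unmatched comparison is not crude: it conditions on race/ethnicity with no region term and gives the same 0.69 and 1.38 points. That stands. The gap is shared, and a reader should not infer that the matched analysis adds a bias from which the primary analysis is free.

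Other points on that side:
- **The SAP does not say that matching ignored region.** It names the variables to be balanced and describes no algorithm, so a within-region restriction is not ruled out. This stands, but the text needs the statement under either reading.
- **The illustration is unfavourable.** The design sought similar racial distribution within region. Race/ethnicity did end up unbalanced, but the documents give neither the size nor the region. Some configurations produce no shift at all. This stands, and the figures show only what is possible.
- **Protection exists already.** The primary analysis keeps all Boston and LA participants who did not opt out, the matched analysis is labelled secondary, and region subgroups give within-region contrasts. This limits the importance, but the overall estimates still lack a region term.

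Three stronger readings are tempting and unsupported. A reader might infer that omitting region is why patients are lost; loss comes from matching itself, and matching within region can lose more. A reader might treat region as the level of allocation; that level is the CHC. A reader might count FIT brand as a background factor thrown out of balance; brand differs by region but belongs to the FIT arm only.

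**Conclusion.** The point holds as a correctable omission of moderate importance. CHCs were allocated within region, yet neither the list of matching variables nor the primary model's covariates includes region. Balancing or adjusting on race/ethnicity or insurance without region can then create a region-driven arm difference. Under the stated assumptions it is about 0.7 to 1.4 percentage points for a regional uptake gap of 10 to 20 points. It is zero when the demographic pattern does not differ by region and arm in the relevant way, or when uptake is the same in both regions. Its actual size, and even its presence, cannot be established from the documents, because they give no counts by CHC, region or arm.

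This does not show that the trial's result is biased, or that the matched analysis has to be abandoned. Replacing it with full-sample regression is a matter of preference.

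**What to change.** 1. In the matched analysis, match exactly within region (Boston, LA), or include region in both the propensity model and the outcome model. Keep CHC as the cluster.
2. State the matching algorithm, ratio and caliper. Report the number dropped per arm and the region share of each arm before and after matching.
3. Add region as a covariate in the primary GEE, for the same reason.
4. Optionally, replace the matched analysis by the GEE on all Boston and LA participants, adjusting for age, gender, race/ethnicity, insurance status and region. This avoids losing patients for want of a match, but relies on the covariate–outcome model.

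The cost is a few lines of SAP text and one re-run on data already held. The drawbacks are one extra model term with only 8 clusters and, if matching is done within region, possibly more unmatched patients.

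### The last SAP analysis adds the non-randomised SD site to the FIT-DNA arm only, with no site or region term stated, so a site difference can shift that contrast; the primary analysis is unaffected

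*SAP*

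**What the plan says.** The Protocol (Design) describes eight cluster-randomised CHCs plus "an additional site in a non-randomized parallel protocol". Its Methods section adds: "Randomization was limited to the 8 CHCs in Boston and LA". SD is the only other location named, so it is the non-randomised site.

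The first paragraph of the SAP sets out the analysis sets. For the RCT, "the primary intent-to-treat analysis included all study participants who did not opt-out from the Boston and LA CHCs". A propensity-matched analysis and a sensitivity analysis on early completers follow, and then: "A final analysis included participants from SD in the FIT-DNA arm". That sentence carries no rationale, label or rule of interpretation, and does not say which outcomes it covers.

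The second paragraph gives one regression model for screening uptake: logistic GEE with CHC as the cluster, "adjusting for age and race/ethnicity, which were unbalanced between the two arms". Region appears as a subgroup factor and in the Fisher tests of colonoscopy completion. It is not named as a term in the model.

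The documents do not settle which tests SD patients received. Under the FIT arm heading the Protocol says "we used the FIT kit brand already in routine use" and lists "LA and SD: Hemosure iFOB test". Its navigation paragraph also allows for abnormal FIT results in SD. The SAP mentions SD only on the FIT-DNA side.

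**The concern.** Adding a non-randomised site to one arm turns a randomised comparison into a mixture of the arm effect and a site effect. Neither feature of the stated model removes the site part. Clustering on CHC deals with standard errors, not with a mean difference at a site that sits in one arm. Adjustment for age and race/ethnicity removes only what those variables explain.

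This analysis closes a list of analyses introduced as belonging to the RCT, so a reader may take it as a robustness check on the randomised result. Agreement or disagreement with the primary result could then reflect the site rather than the outreach strategy, and the SAP gives no guidance on reading it.

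**Working it through.** **Inputs.** From the documents: eight randomised CHCs, four per region, split between two arms; SD not randomised; SD added to FIT-DNA only; covariates age and race/ethnicity. No uptake rate, ICC, SD sample size or working correlation is given, and there is no stated figure to reproduce. Everything numerical below is assumed and shows mechanism and range only.

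**1. Size of the shift.** To a good approximation, shift = (weight of SD in the FIT-DNA arm) × (SD uptake difference left after adjustment). With four randomised FIT-DNA CHCs of 500 patients,

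weight = w(n_SD) / [4·w(500) + w(n_SD)], where w(n) = n / [1 + (n − 1)·ICC].

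ICC = 0 gives the independence weights, and ICC = 0.01 illustrates an exchangeable structure. For example, with n_SD = 250 and ICC 0.01: w(250) = 250/3.49 = 71.6, w(500) = 500/5.99 = 83.5, and the weight is 71.6/(333.9 + 71.6) = 0.177.

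| SD patients | Weight, independence | Weight, ICC 0.01 | Shift for a 10-point residual, independence / ICC 0.01 |
|---|---|---|---|
| 250 | 0.111 | 0.177 | 1.1 / 1.8 points |
| 500 | 0.200 | 0.200 | 2.0 / 2.0 points |
| 1000 | 0.333 | 0.214 | 3.3 / 2.1 points |
| 2000 | 0.500 | 0.222 | 5.0 / 2.2 points |

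**2. On the odds-ratio scale.** Take 30% uptake in both randomised arms (no true effect), weight 0.20, and SD 10 points higher or lower. The pooled FIT-DNA arm is then 32% or 28%:

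- (0.32/0.68)/(0.30/0.70) = 1.10
- (0.28/0.72)/(0.30/0.70) = 0.91

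**3. What a region term does.** Logistic regression on expected counts: eight CHCs of 500, SD of 500, FIT uptake 30% in Boston and 25% in LA, true odds ratio 1.30.

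| SD uptake | Pooled odds ratio, no region term | With region term |
|---|---|---|
| 20% | 1.15 | 1.30 |
| 30% | 1.26 | 1.30 |
| 40% | 1.38 | 1.30 |

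With the region term, the standard error of the log odds ratio is 0.0692, identical to Boston and LA alone. A site with one arm contributes nothing to the arm effect once its own level is fitted. The pooled contrast is therefore either open to site confounding or no more informative than the randomised analysis, unless SD also supplies FIT recipients.

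**4. Does covariate adjustment rescue it?** A GEE simulation assumed 4 versus 4 CHCs of 400, 30% uptake, no arm effect, SD differing in age and race mix plus a residual 10 points down or up, and adjustment for age and race (120 runs per setting). Boston and LA only gave odds ratios of 0.98 to 1.01. With SD pooled into FIT-DNA:

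- independence: 0.90 / 1.10 (SD n = 400) and 0.83 / 1.19 (SD n = 1000)
- exchangeable: 0.91 / 1.09 (SD n = 400) and 0.89 / 1.11 (SD n = 1000)

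**The case against.** **The model is inferred.** The SAP does not say that the pooled analysis lacks a site term; it describes one model and gives no separate specification. This stands as a limit on wording: no such term is stated. It does not rescue the analysis, because a site term would leave SD contributing nothing to the arm effect unless FIT recipients there were included.

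**Ten points is a large gap.** At 30% uptake and ICC 0.01 the between-site standard deviation is √(0.01 × 0.21) = 4.6 points, so 10 points is about 2.2 standard deviations. A site one standard deviation away, at weights of 0.18 to 0.22, shifts the contrast by 0.8 to 1.0 points. The standard error of the randomised difference with 4 versus 4 CHCs of 500 is √(2 × 0.21 × 5.99/2000) = 3.5 points. This is fair context: the shift may be small beside ordinary noise, and the 5.0-point end needs several unfavourable assumptions together. But SD is not a random draw from the same regions, and the shift is a bias that larger CHC samples do not remove.

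**The simulation looks too clean.** A Monte Carlo standard error of 0.007 over 120 runs implies about 0.077 per run, which is binomial error alone, so CHC-to-CHC variation seems to have been left out. A repeat with ICC 0.01 gave the same mean shift: odds ratios of about 0.90 and 1.09, against about 1.0 for the randomised CHCs alone.

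**Much is already in place.** The primary set excludes SD, and the Protocol calls the additional site non-randomised. Both are true, and they confine the problem to one analysis. They do not tell the reader how to interpret it.

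**Other SD matters are separate.** Usual-care follow-up in SD comes after an abnormal stool test and would not itself move 90-day uptake. The FIT brand entry may record only the kit in routine use. Neither adds weight to the bias argument. The first is a reason to keep SD follow-up apart, and the second must be clarified because it decides whether any within-SD contrast exists.

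**Conclusion.** The concern holds. As written, the supplementary contrast combines a randomised comparison with a site difference that the stated covariates remove only in part. The structure is clear from the documents; size and direction are not. On the assumptions above, a 10-point residual shifts the contrast by 1.1 to 5.0 points (independence) or 1.8 to 2.2 points (exchangeable, ICC 0.01), and a gap of one between-site standard deviation by about 1 point under the exchangeable weights. With no residual difference the shift is zero. The primary intent-to-treat result is untouched. The change should be made, but it does not threaten the trial's main conclusion.

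**What to change.** - Restrict between-arm inference to the randomised Boston and LA CHCs.
- Report SD uptake descriptively as a separate non-randomised cohort. Report SD colonoscopy follow-up separately too, since SD had usual-care follow-up rather than the standardised navigation.
- The SAP uses the past tense, so the pooled analysis may already have been run. If so, disclose it labelled as non-randomised, exploratory and confounded by site, state the model used, and do not cite it for or against the randomised result.
- Reconcile the Protocol and SAP on whether SD had FIT recipients. If it did, report the within-SD contrast separately, labelled non-randomised.

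The cost is a few sentences in the SAP and one supplementary table restructured. No randomised information is lost, and nothing already produced is withheld.

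### The primary GEE on 8 CHCs states no small-sample method and leaves out the region stratum, so its nominal 5% error rate is not assured in either direction

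*SAP*

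**What the plan says.** The Protocol (Methods, randomisation paragraph) fixes the number of clusters: "Randomization was limited to the 8 CHCs in Boston and LA". Allocation was regional: "Within each region, we considered the permutations of assigning the four CHCs into two arms". One split was kept on balance grounds: "We chose the permutation with the closest patient volume, racial distribution, and baseline CRC screening rate". The investigators "then randomly assigned the groups to one of the two study arms".

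The outcome at stake is in the Protocol's Objective: "The primary outcome was CRC screening test completion rate using any screening modality (FIT, FIT-DNA, colonoscopy) at 90 days" from mailing of the test.

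The SAP's second paragraph compares the arms at 90 and 180 days "using logistic regression models with the generalized estimating equations to account for the correlated nature of data within CHCs". Only two covariates are listed for this model, and the reason for them is given: "adjusting for age and race/ethnicity, which were unbalanced between the two arms". Region appears only in the subgroup and colonoscopy analyses. CHC baseline screening rate and patient volume appear in no listed model. The software is named (SAS 9.4), but no procedure or option. Alpha, sidedness, working correlation, variance estimator, degrees of freedom and small-sample correction are not stated.

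**The concern.** The sandwich variance behind GEE is justified when clusters are many. With 8 it tends to be too small, and the normal reference distribution ignores how poorly it is estimated. A test run that way rejects too often.

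The design pulls the other way. Each arm takes CHCs from both regions, so a Boston–LA difference largely cancels from the arm contrast. If region is not modelled, that difference stays in the between-CHC residuals and widens the standard error. Choosing the split on baseline screening rate has a similar effect: it makes the arm contrast less variable than the residuals suggest.

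At stake are the p-value and interval for the primary outcome and for the 180-day outcome. The propensity-matched, 7-day-exclusion and SD-added analyses are not said to use a different inference method.

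**Working it through.** **Inputs.** From the Protocol: 8 CHCs, 4 per region, one split kept per region and then randomised to arms. Two against two within region is implied by the balancing but not stated. The documents give no planned error rate, power, ICC, CHC size or completion rate, so there is no figure of the plan's own to reproduce. Assumed here: two-sided 5%, uncorrected sandwich z-test, 30% completion, ICC 0.01–0.05, mean 400 patients per CHC, and a baseline rate correlating 0.5–0.9 with the CHC's true log-odds.

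**1. Few clusters alone (equal sizes, no matching, no regional gap).** Let SS be the residual sum of squares of the 8 CHC log-odds.
- Arm only: sandwich variance of the arm difference = SS/16; unbiased variance = (SS/6)(1/4 + 1/4) = SS/12. The ratio is 12/16 = 6/8. True size = P(|t6| > 1.96·√(6/8)) = 14.05%.
- Arm and region: unbiased variance = SS/10, ratio 5/8. True size = P(|t5| > 1.96·√(5/8)) = 18.2%.

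**2. Effect of an unmodelled regional gap.** Let v be the variance of a CHC log-odds within region and d the Boston–LA gap in log-odds. The gap adds 8(d/2)² = 2d² to SS. Expected sandwich variance over true variance is then (6v + 2d²)/(8v) = 0.75 + d²/(4v).
- ICC 0.01: v = 0.01/0.21 + 1/(400×0.21) = 0.0595. The ratio is 0.75 at d = 0, 1.42 at d = 0.4 and 2.81 at d = 0.7.
- ICC 0.05: v = 0.05/0.21 + 1/(400×0.21) = 0.25. The ratio is 0.75, 0.91 and 1.24.

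A ratio below 1 makes the standard error too small and above 1 too large. Both occur within plausible inputs, before the matched split lowers the true variance further.

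**3. Simulated size of the analysis as described, matched split.**

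| CHC sizes, working correlation | No gap | Gap 0.4 | Gap 0.7 |
|---|---|---|---|
| Equal | 2–12% | 1–9% | 0–5% |
| 100/250/400/850 per region, exchangeable | 3–18% | 2–11% | 0.4–7% |
| 100/250/400/850 per region, independence | 11–21% | 8–17% | 3–13% |

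A second simulation used other assumptions: 25% completion, mean 500 per CHC, coefficient of variation 0.4, independence, correlation 0.7. It gave 10.3–12.0% with no gap, 3.3–6.9% at a gap of 0.5 and 0.3–3.2% at 1.0.

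**4. Randomisation test.** Once one split per region is fixed, each region has 2 possible assignments. If the regions were assigned separately there are 2 × 2 = 4. Each assignment has a mirror image with the same absolute difference, so the smallest two-sided p-value is 2/4 = 0.5. The inference therefore rests on the model.

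**5. Alternatives, simulated size with a matched split.**

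| Analysis | Size |
|---|---|
| GEE with region, uncorrected z | 3–15% equal sizes, 5–24% unequal |
| GEE with region and baseline rate, uncorrected z | 23–26% equal, 27–33% unequal |
| CHC-level with region, t on 5 df | 0.3–4.4% (0.2–6.1% in a repeat) |
| GEE with region, Mancl–DeRouen, t on 5 df | 0.7–1.3% |
| CHC-level with region and baseline rate, t on 4 df | 4.2–5.6% (3.9–5.7% in repeats) |
| GEE with region and baseline rate, Mancl–DeRouen, t on 4 df | 1.4–2.5% |
| GEE with region and baseline rate, Kauermann–Carroll, t on 4 df | 5–7% equal, 7–9% unequal |

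**The case against.** The SAP is a two-paragraph summary. A corrected variance or a score test may have been used in SAS without being mentioned. That stands: what is shown is an unspecified method, not a test known to be invalid.

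A reader might infer that leaving out region and baseline rate inflates the false-positive rate. The documents do not support that. Step 2 shows that an unmodelled regional gap widens the standard error, and balancing on baseline rate also makes the test conservative. The inflation risk comes from the missing small-sample correction; the omitted terms cost power. Adding them uncorrected makes matters worse. The patient-level race/ethnicity term also partly covers one of the three balancing factors.

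The sizes rest entirely on assumed inputs. The 21% upper end needs independence working correlation and very uneven CHCs (coefficient of variation 0.70). Balancing volume between groups does not settle variation within them, and the documents give no CHC sizes. This too stands, so no single error rate can be quoted.

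Finally, making a 4-df CHC-level analysis primary would partly be a matter of preference. With no weighting it targets a CHC-average effect, whereas the SAP compares proportions of individuals. Its power advantage also depends on how well baseline rate predicts outcome. For an assumed 30% v 40%, matched on baseline rate with equal sizes, no correlation gives 49% v 54% on 4 and 5 df at ICC 0.01, 31% v 34% at 0.02 and 16% v 17% at 0.05. From a correlation of 0.5 upward, 4 df was better in every setting tried. That is a reason to keep it as a sensitivity analysis.

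**Conclusion.** The point holds and should be fixed. With 8 clusters and no stated small-sample method, the primary and 180-day p-values and intervals cannot be relied on at a nominal 5% or reproduced from the SAP. Region, the allocation stratum, also belongs in the model.

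Under an uncorrected sandwich z-test, few clusters alone give about 14% (equal sizes, no matching, no gap). Matching and a regional gap can bring this to near 0%. The net direction depends on the ICC, CHC sizes, regional gap and predictive strength of baseline rate, none of which the documents give. A reader might conclude that a positive primary result would be a false positive, or that the trial used an invalid test; neither follows. The 5% level, the z-test, two-against-two splits and separate assignment by region are all assumptions.

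**What to change.** In the SAP's second paragraph:
- State two-sided alpha and the working correlation, and add region (Boston/LA) to the primary 90-day and the 180-day models.
- Base the p-value and 95% CI on one named method for 8 clusters, with t on 5 df (8 CHCs minus intercept, arm and region). One option is the GEE with a named small-sample-corrected variance. The other is a two-stage analysis: patient-level logistic regression on CHC indicators, age and race/ethnicity without arm, then linear regression of the 8 adjusted log-odds on arm and region. If stage two is unweighted, say that it targets the CHC-average effect.
- Report as a sensitivity analysis the version that also adjusts for CHC baseline screening rate, with t on 4 df.
- Do not add region or baseline rate to the GEE without the correction.
- Present the region-specific (2 v 2) estimates descriptively.

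The SAP is written largely in the past tense. The main route is therefore to report the existing and corrected analyses side by side, labelling the correction post hoc unless it was in fact pre-specified.

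The cost is SAP wording and a rerun on existing data; baseline rates are held, since they were used to choose the split. Critical values rise from 1.96 to 2.57 (5 df) or 2.78 (4 df). The 5-df analysis is conservative if the matching worked.
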